7.3 ENDPOINTS

The following are the planned endpoints for the study:

7.3.1 PRIMARY SAFETY ENDPOINT:

- Freedom from all-cause mortality, disabling stroke and life-threatening bleeding at 30 days post-implant.

7.3.2 PRIMARY PERFORMANCE ENDPOINT:

- Procedure success at 30 days post-treatment, as measured by: technical success with reduction of MR to less than or equal to mild and the absence of major device or procedure-related SAEs.

7.3.3 OTHER PLANNED ANALYSES:

- Technical success defined as survival and exit from the operating room (OR) with successful implantation of 3 or more expanded polytetrafluoroethylene (ePTFE) chords
- Freedom from major device or procedure-related serious adverse event (SAE) at 30 days, 1 year and 2 years post-implant
- Quality of Life (change from baseline to 1 and 6 months)
- 6-minute walk test (change from baseline to 1 and 6 months)
- Freedom from ePTFE chord rupture as reported by echo core lab at 1 year and 2 years post-implant
- Freedom from reoperation or re-intervention due to ePTFE chord rupture at 1 year and 2 years post-implant
- Functional improvement from baseline NYHA Functional Classification at 1 year and 2 years post-implant
- Freedom from reoperation or reintervention on the mitral valve annually through 5 years post-implant
- Freedom from \geq moderate MR annually through 5 years post-implant

7.3.4 KEY ENDPOINT DEFINITIONS:

A complete list of definitions can be found in **Attachment A**. Key endpoint definitions include:

All-cause mortality:

Mortality for any cause will be reported with a further stratification by Cardiovascular and Non-Cardiovascular. All Deaths will be adjudicated for a cause of death and relationship to the investigational device and the index/implant procedure.

Cardiovascular mortality

Expirations for any of the contributing conditions such as Heart failure, Myocardial infarction, Major bleeding, Thromboembolism, Stroke, Arrhythmia and conduction system disturbance, Cardiovascular infection and sepsis (e.g., mediastinitis and endocarditis), Tamponade, Sudden, unexpected death Other cardiovascular, Device failure, Death of unknown cause (adjudicated as cardiovascular)

Noncardiovascular mortality

Any death in which the primary cause of death is clearly related to another condition such as Non-cardiovascular infection and sepsis (e.g., pneumonia,) Renal failure, Liver failure, Cancer, Trauma, Homicide, Suicide, Other non-cardiovascular causes.

Disabling Stroke

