Stroke is defined as a focal or global neurological deficit lasting more than 24 h OR less than 24 h if available neuroimaging documents a new intracranial or subarachnoid hemorrhage (hemorrhagic stroke) or central nervous system infarction (ischemic stroke) OR the neurological deficit results in death.

A disabling stroke includes any neurological deficit (for example partial visual field cut) with a modified Rankin scale score equal or more than 2 with an increase in equal 1 or more modified Rankin scale score category from individual's pre-stroke baseline at 90 days after stroke onset.

Life-threatening Bleeding

Bleeding in a critical organ, such as intracranial, intraspinal, intraocular, intrathoracic, or pericardial necessitating surgery or intervention, or intra- muscular with compartment syndrome *OR* bleeding causing hypovolemic shock or hypotension (systolic blood pressure <90 mm Hg lasting >30 min and not responding to volume resuscitation) or requiring significant doses of vasopressors or surgery.

Fatal Bleeding: Bleeding adjudicated as being a proximate cause of death. Severe bleeding adjudicated as being a major contributing cause of a subsequent fatal complication, such as MI or cardiac arrest, is also considered fatal bleeding.

Major device or procedure related serious adverse event

All Major Serious Adverse Events adjudicated as device or procedure related, as defined by modified MVARC (Stone, et al.) including:

- Procedure or Device related Death
- Procedure or Device related Stroke
- Procedure or Device related Life-threatening bleeding (MVARC scale)
- Major vascular or access (index procedure) complications
- Major cardiac structural complications related or cause by device or procedure
- Procedure related Stage 2 or 3 acute kidney injury (includes new dialysis)
- Procedure related Myocardial infarction or coronary ischemia requiring PCI or CABG
- Procedure or device related severe hypotension, heart failure, or respiratory failure requiring intravenous pressors or invasive or mechanical heart failure, treatments such as ultrafiltration or hemodynamic assist devices, including intra-aortic balloon pumps or left ventricular or biventricular assist devices, or prolonged intubation for more than 48 h.
- Any device-related dysfunction, migration, thrombosis, or other complication requiring surgery or repeat intervention including:

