9.4 BASELINE/PRE-PROCEDURE EVALUATIONS

Once the subject has signed a study informed consent, data from the following assessments which would have already been conducted as part of the standard of care, will be recorded:

- Routine laboratory assessment (recording any of the following that are done as part of the standard of care: WBC count; haemoglobin haematocrit, platelet count, creatinine, INR, total albumin, total bilirubin, BNP, NTproBNP)
- Routine electrocardiogram (ECG)
- Routine physical examination
- Assessment of NYHA Heart Failure Class
- Transthoracic echocardiogram (TTE)
- 3D Transoesophageal echocardiogram (TOE)
- Patient Eligibility Committee report of the TOE
- Assessment of Medical History

The following baseline assessments will be conducted as part of the study following informed consent.

- Assessment of STS score risk
- Assessment of EURO score risk
- 6 Minute Walk Test
- Quality of Life Assessment - SF-36
- Quality of Life Assessment - KCCQ
- Assessment of cardiac medications
- Pregnancy test (if applicable)

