9.5.3 PRIMARY FOLLOW-UP ASSESSMENTS

Post-procedure management: Standard hospital protocols for the management of subjects after mitral valve surgery shall be followed.

7-Day/Discharge assessment: All subjects shall be discharged from the hospital at the discretion of the attending cardiac surgeon. Prior to discharge, all subjects shall undergo a comprehensive pre-discharge TTE as well as a physical exam on either day 7 or at the time of discharge, whichever occurs first.

Primary subject follow-up: Subjects shall be seen at 30 days (+20/-0 days) after the HARPOON System procedure. A TTE and specific clinical assessments, in accordance with the Schedule of Assessments, shall be performed at that time.

Additional clinical and TTE follow-up shall occur for all active subjects in accordance with the Schedule of Assessments at the following intervals:

- 6-months (+/- 30 days)
- 12-months (+/- 30 days)
- 18-months (+/- 30 days)
- 24-months (+/- 60 days)
- 36-months (+/- 60 days)
- 48-months (+/- 60 days)
- 60 months (+/- 60 days)

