Maximal change in sCr from baseline to 7 days post-procedure:

- Stage 1: Increase in sCr to 150%–199% (1.50–1.99 x increase vs. baseline), increase of ≥ 0.3 mg/dl (≥ 26.4 mmol/l) within 48 h, or urine output < 0.5 ml/kg/h for ≥ 6 h but < 12 h

- Stage 2: Increase in sCr to 200%–299% (2.00–2.99 x increase vs. baseline) or urine output <0.5 ml/kg/h for ≥12 h but <24 h
- Stage 3: Increase in sCr to ≥300% (>3.0 x increase vs. baseline), sCr of ≥4.0 mg/dl (≥354 mmol/l) with an acute increase of ≥0.5 mg/dl (44 mmol/l), urine output <0.3 ml/kg/h for ≥24 h, or anuria for ≥12 h; patients receiving renal replacement therapy are considered stage 3 irrespective of other criteria

ARRHYTHMIAS AND CONDUCTION SYSTEM DISTURBANCES

For emerging mitral valve procedures in which the frequency of major arrhythmias and conduction system disturbances is unknown, continuous rhythm monitoring for at least 48 h in the post-procedural period is recommended to maximize the detection of arrhythmias and conduction system disturbances. Data elements to be collected for all patients should include:

- Baseline conduction abnormalities, paroxysmal or permanent atrial fibrillation (or flutter), ventricular arrhythmias, and the presence of permanent pacemaker and implantable defibrillators. The type of permanent pacemaker should be recorded (e.g., single vs. dual chamber, biventricular).
- Procedure-related new or worsened cardiac conduction disturbance (including first-, second-[Mobitz I or Mobitz II], or third-degree AV block; incomplete and complete right bundle branch block; intraventricular conduction delay; left bundle branch block; left anterior fascicular block; or left posterior fascicular block, including heart block) requiring a permanent pacemaker implant; each subclassified as persistent or transient
- New-onset atrial fibrillation (or flutter) which lasts sufficiently long to be recorded on a 12-lead electrocardiogram, or at least 30 s on a rhythm strip.
- New-onset ventricular tachycardia or fibrillation
- Pacemaker or defibrillator lead dislodgement

Arrhythmias and conduction system disturbances are subclassified according to:

- The occurrence of hemodynamic instability
- Need for therapy including electrical/pharmacological cardioversion or initiation of a new medication (oral anticoagulation, rhythm, or rate control therapy)

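### Stage 2-3 acute kidney injury counts against the primary performance endpoint, but no creatinine or urine output is scheduled after the procedure from which to grade it

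*Combined protocol and SAP*

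**What the plan says.** Section 7.3.2 defines the primary performance endpoint, procedure success at 30 days, as "technical success with reduction of MR to less than or equal to mild and the absence of major device or procedure-related SAEs". The list of such events in section 7.3.4, repeated in Attachment A, includes "Procedure related Stage 2 or 3 acute kidney injury (includes new dialysis".

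Attachment A stages AKI on this basis: "Maximal change in sCr from baseline to 7 days post-procedure". Stage 2 is defined by a creatinine ratio or by urine output: "Stage 2: Increase in sCr to 200%–299% (2.00–2.99 x increase vs. baseline) or urine output <0.5 ml/kg/h for ≥12 h but <24 h". Stage 3 can be met by a ratio of at least 300%, by an absolute level with an acute rise ("sCr of ≥4.0 mg/dl (≥354 mmol/l) with an acute increase of ≥0.5 mg/dl (44 mmol/l"), by urine output, by anuria or by renal replacement therapy. Stage 1, which is not an endpoint component, also has an absolute criterion: "increase of ≥ 0.3 mg/dl (≥ 26.4 mmol/l) within 48 h".

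On data collection, the laboratory row of Table 3 is marked once, in the baseline column, and its footnote 3 limits it to standard-of-care tests, where done. Section 9.4 agrees: for laboratory values, "data from the following assessments which would have already been conducted as part of the standard of care, will be recorded". For the 7-day or discharge visit, section 9.5.3 says that "all subjects shall undergo a comprehensive pre-discharge TTE as well as a physical exam on either day 7 or at the time of discharge". It names no laboratory test.

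**The concern.** An outcome defined by a change in a laboratory value needs at least one value before and one after. The plan collects the first only if it happens to exist, and does not schedule the second. Urine output, the alternative criterion, is not scheduled at any visit.

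Many other entries on the major-event list are tied to something hard to overlook, such as death, surgery, a reintervention or a mechanical support device. Stage 2 AKI, and Stage 3 reached on creatinine alone, need no treatment to qualify. Someone has to look at the creatinine series and report what it shows.

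Where nobody does, the subject has no recorded major event and is counted as a procedure success. The error can run only one way, towards a higher success rate. The same gap affects freedom from major device- or procedure-related events at 30 days, 1 year and 2 years, because an AKI missed in the first week stays missed.

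**Working it through.** **1. From the endpoint to the data**

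- Needed to stage AKI on creatinine: a baseline value and the highest value through day 7 (Attachment A).
- Baseline value: recorded if routine care produced one (Table 3 footnote 3; section 9.4).
- Value at surgery, at 7 days or discharge, or at 30 days: none scheduled (Table 3; section 9.5.3).
- Urine output: none scheduled at any visit.

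Scheduled data therefore give at most one creatinine value per subject, and a change cannot be computed from one value. The remaining routes are adverse event reporting (sections 11.1 and 11.3.1), monitoring and the review of source documents (section 11.3.2), and index-admission records kept at the site (section 14.5.1).

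The grader is also unclear. Section 7.3.4 requires major events to be adjudicated as related, but the synopsis and section 11.3.2 describe the Clinical Events Committee's scope as death, stroke, bleeding and reintervention. AKI is not named.

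**2. Scale**

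- One missed case, in a subject who otherwise meets the endpoint and with all 250 in the denominator: 1/250 = 0.4 percentage points of procedure success.
- The nearest prior figure is early renal failure in Table 1: 0/62 = 0.0%, as printed. The exact two-sided 95% upper limit is 1 − 0.025^(1/62) = 0.0578, or about 5.8%. This is not the Stage 2-3 AKI definition, so it shows only that the earlier experience is too small to rule out a non-trivial rate.
- The documents give neither a Stage 2-3 AKI rate nor a rate of non-reporting. The bias cannot be computed from them.

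**3. The SI units (secondary)**

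Assumption: molar mass of creatinine 113.12 g/mol, a physical constant not in the documents. Values of 113.0 to 113.2 lead to the same conclusion. Formula: mmol/l = (mg/dl × 10) / 113.12.

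| Criterion | Printed SI value | Computed from mg/dl | Printed SI number ÷ mg/dl |
|---|---|---|---|
| Stage 3, 4.0 mg/dl | 354 mmol/l | 0.3536 mmol/l = 353.6 micromol/l | 88.5 |
| Stage 3, 0.5 mg/dl | 44 mmol/l | 0.0442 mmol/l = 44.2 micromol/l | 88.0 |
| Stage 1, 0.3 mg/dl | 26.4 mmol/l | 0.0265 mmol/l = 26.5 micromol/l | 88.0 |

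The printed equivalents do not reproduce in mmol/l. Taken literally, 354 mmol/l is 354 × 113.12 / 10 = about 4,004 mg/dl. Relabelled as micromol/l, all three numbers agree with their mg/dl values to within about 0.5%. The numbers are right and the unit, as it appears in the text, is wrong by a factor of 1000.

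**The case against.** The strongest reply is that capture through adverse events is the study's general design and is not left to chance. Table 4 counts abnormal laboratory findings as adverse events, Table 3 records events from the day of surgery, serious events must be notified within 3 calendar days, a contract research organisation monitors for complete reporting, and the committee may identify unreported events in the documents it reviews. Myocardial infarction is likewise defined by biomarkers that are not scheduled. The committee charter, the case report form and the separate SAP mentioned in section 10.6.4 are not available here, and may contain AKI fields.

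Much of this stands. A reader might infer that AKI staging rests only on what an investigator chooses to report; the documents do not support that. What the safeguards lack is a systematic step. Source documents are requested for events already identified as possible endpoints, so this route does not screen the remaining subjects for a creatinine doubling that no one reported.

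Three other stronger readings also go too far:

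- **Every Stage 2-3 creatinine change is an endpoint failure.** It counts only as a major serious event judged related to the procedure.
- **The unit error makes Stage 2-3 ungradable at SI sites.** Stage 2 has no SI threshold, Stage 3 has several other routes, and the correct mg/dl figure is printed first in each criterion. The letter m may also be a micro sign lost when the PDF was read, and its appearing three times does not exclude that.
- **The number of lost failures can be stated.** Any such number needs an assumed incidence and an assumed non-reporting rate, and the documents support neither.

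**Conclusion.** The point holds as an ascertainment gap. A named component of the primary performance endpoint is defined by a laboratory change that the scheduled data cannot show, and missed cases count as successes. The direction, in the device's favour, follows from the design. The size does not: 0.4 percentage points per missed case is arithmetic, but the number of such cases is unknown.

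The effect on conclusions is probably limited. The primary endpoints are summarised with confidence intervals and no stated success threshold, and section 10.2.1 aims for a precision of 5% or better. This is a worthwhile, inexpensive improvement and does not undermine the study. The conclusion assumes that no document outside those available already requires post-procedure creatinine.

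The unit mismatch is close to clerical and depends on what the original page prints.

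**What to change.** In Table 3 and the case report form, add:

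- the last creatinine before the procedure;
- the highest creatinine obtained in routine care through day 7 or discharge;
- any dialysis in that period.

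Derive the AKI stage from these values. Send Stage 2-3 cases for adjudication of procedure relatedness, and state which body does this. Report the number of subjects with no post-procedure value, so that a reader can see how much of the endpoint rests on event reporting alone.

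Separately, check the original page of Attachment A. If it prints mmol/l, change the unit to micromol/l in the Stage 1 and Stage 3 absolute criteria, and in the committee charter if it repeats them.

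The cost is a few fields filled from existing hospital results and a small addition to the adjudication workload. No new test is needed. Procedure success may come out slightly lower.
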